### **C. Treatment assignment/randomization**

Participants will be randomized to receive one of three conditions: (1) the PP-based intervention, (2) an MI-based educational control condition, or (3) TAU. They will be randomized by a random-number generator and will be assigned a condition after Actigraph data is checked and has been found to be adequate at in-hospital Visit #2. The research assistant (RA)/blinded assessor who will conduct the follow-up assessments will be blind to the study condition. The interventionist and subjects will not be blind to the study condition.

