#### **Second Visit (Week 2; in person).**

At the second in person visit, which will take place one week after the initial visit, we will collect the Actigraph from participants, and check to ensure participants had at least 5 valid days of data. At this point, participants will be randomized to one of the three conditions noted above. Patients in the TAU group will receive no further intervention and will be scheduled for a follow-up appointment in 12 weeks. Participants in the PP and goal-setting or MI-only conditions will be provided with a manual corresponding to their treatment condition, as well as a copy of *Learning to Live with Heart Failure*, a practical guide which is provided by MGH to all HF patients admitted to a cardiology unit at MGH.

**PP and goal-setting intervention:** The trainer then will introduce the participant to the PP and goal-setting portions of the intervention. For the PP portion, participants will be assigned the first exercise (Gratitude for Positive Events) and will be instructed to perform the exercise within the next week. Prior to completing the exercise, participants will be asked to rate their current level of happiness and optimism, using a 10-point Likert scale. Immediately after completing the

exercise, participants will rate the ease of exercise completion, overall utility of the exercise, and their current levels of happiness and optimism, all using 10-point Likert scales. For the first goal-setting session, the trainer will discuss the importance of physical activity in HF. Participants will be given a pedometer, which participants will use to monitor the number of steps they take daily over the following week. The trainer will instruct them in its use and set a goal for monitoring their baseline physical activity over the next week. This pedometer will not be used as an outcome measure but simply will be a tool that participants can use to monitor their activity.

*MI-based educational intervention:* Participants in the MI-only control group will similarly have the rationale of the MI-based health behavior program explained to them, and will be assigned the first exercise. They also will be given a pedometer for their personal use. We estimate that this portion of the visit will take approximately 20 minutes.

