#### Measures:

- Optimism: LOT-R; SOM
- Positive affect: PANAS (primary outcome measure for this aim)
- Anxiety/depression: HADS

We will examine between-group differences (PP-based condition vs. MI-informed educational control and PP-based condition vs. TAU) on changes in each of these psychological outcomes to assess the impact of the intervention compared to both an active control and TAU. The primary study endpoint will be 12 weeks, though we will secondarily assess the impact of the intervention on outcomes at 24 weeks as well.

**Aim #3 (Impact on functional outcomes and health behaviors):** To examine the impact of the intervention on physical activity (steps, as measured by accelerometer; primary health behavior outcome), medication adherence, sodium intake, HF-related QoL, and generic HRQoL, compared to treatment as usual and an MI-based health behavior education intervention.

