**Measures:**

- HF-related QoL: KCCQ
- HF symptoms: KCCQ subscale
- Health related quality of life: SF-12
- Self-reported adherence: MOS
- Physical activity: ActiGraph accelerometer
- Medication adherence: SRMA
- Sodium intake: SSQ

We will examine between-group differences (PP-based condition vs. MI-informed educational control and PP-based condition vs. TAU) on changes in functional outcomes and health behaviors to assess the impact of the intervention compared to both an active control and TAU.

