**C. Statistical methods**

Data will be downloaded from REDCap into the Stata statistical package. For Aim 1 (feasibility, acceptability), descriptive statistics will be used to report proportion of exercise completion and mean scores on exercise ratings of ease and utility. To examine the immediate impact of the intervention on positive affect and optimism, we will use linear mixed models (to account for within-person correlations) to examine the improvement in these scores from pre- to post-exercise.

For our secondary aims, we will initially compare physical activity (# of steps/day) at 12 and 24 weeks between groups using a Wilcoxon rank sum test, given that the distribution of the number of steps will likely be skewed. In addition, we will compare between-group differences in change over time in all self-report measures (including psychological, functional, and health behavior outcomes) at the 12 and 24-week time points using random effects regression models with a random intercept for each patient. All statistical tests will be two-tailed, with  $p < .05$  considered significant.

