**D. Power analysis**

We have performed power analyses assuming 20 participants in each group. To account for potential drop outs between enrollment and randomization, we will enroll 75 participants with a goal of randomizing 60. This pilot trial is not designed to detect significant between-group differences in 12- or 24-week health behavior outcomes, but is powered to meet our primary aims of feasibility and immediate impact. For feasibility, 75-80% of subjects have completed the majority of PP exercises in our prior work, and 90% completed the majority of PP exercises in our proof-of-concept trial in patients with HF. With 20 PP participants, we will have at least 80% power to detect a difference between our expected proportion of participants completing at least 5 out of 8 PP exercises (80%) and the null hypothesis (true proportion of 50% or less) at the

two sided 0.05 level using a binomial proportion test. In a prior study, we found that PP interventions led to a moderate ( $d=.52$ ) improvement in optimism immediately post-exercise. If we assume completion of ~140 exercises from 20 subjects and a within-person correlation of 0.5 for change in pre-/post- ratings across exercises, our proposed study is powered at over 80% to detect a similar effect size improvement of optimism immediately post-exercise at the two-sided 0.05 level.

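### Steps per day, the primary health behaviour outcome: the plan disagrees on level versus change, and the one named test omits a baseline that every randomised participant must have

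*Combined protocol and SAP*

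**What the plan says.** Section VI.A and B, Aim 3, names accelerometer steps as the primary health behaviour outcome and lists the ActiGraph among the measures. It then says that PP versus MI and PP versus TAU will be compared "on changes in functional outcomes and health behaviors to assess the impact of the intervention compared to both an active control and TAU". The Aim 3 hypothesis in Section II is likewise framed as improvement.

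Section VI.C gives the method for steps in one sentence: "we will initially compare physical activity (# of steps/day) at 12 and 24 weeks between groups using a Wilcoxon rank sum test", and the reason is "given that the distribution of the number of steps will likely be skewed". The next sentence introduces random effects regression with a random intercept, but for "between-group differences in change over time in all self-report measures", which leaves out an accelerometer outcome. No second analysis of steps follows the initial one.

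Baseline steps are collected before assignment. Under Section IV.C participants "will be assigned a condition after Actigraph data is checked and has been found to be adequate at in-hospital Visit #2". Under Section V.A (Second Visit) staff "check to ensure participants had at least 5 valid days of data", and Section V.E adds a re-wear rule for participants who fall short.

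Two other statements bear on the point. The Aim 2 text says "The primary study endpoint will be 12 weeks". Section VI.D says "This pilot trial is not designed to detect significant between-group differences in 12- or 24-week health behavior outcomes".

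**The concern.** Two analysts following this plan could run different tests. One would rank steps at week 12 and week 24 and ignore baseline, as Section VI.C reads literally. The other would rank changes from baseline, to honour the Aim 3 text. Nothing in the plan settles the choice, so it could be made after the data are seen.

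Neither analyst would use baseline as a covariate, although it is in hand for everyone randomised. Skewness is the only reason offered for the rank test, and it does not require dropping baseline: steps can be transformed, or ranks can be adjusted for baseline ranks.

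Because the pilot claims no power for health behaviours, its useful product for steps is an effect estimate with its uncertainty, to inform a later trial. The plan specifies neither an estimate nor an interval alongside the test, and leaving baseline out widens any interval derived from the data.

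**Working it through.** **Stated figures.** The plan gives no power or precision figure for steps, so there is none to reproduce. Its feasibility power does reproduce: with 20 participants, a cut-off of 15 or more gives two-sided alpha 0.041 and power 0.804. This point does not affect it.

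**Inputs.** 20 per arm and two-sided 0.05 (Sections VI.D and VI.C). The correlation r between baseline and follow-up steps is not in the documents and is assumed to be 0.3 to 0.8. The low end allows for inpatients, whose baseline week may include or follow a hospital stay. Results are in SDs of log steps.

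**Variance of a between-arm difference, relative to follow-up only.**
- Baseline as covariate (ANCOVA): 1 − r². At r = 0.7, 1 − 0.49 = 0.51.
- Change score: 2(1 − r). At r = 0.7, 2 × 0.3 = 0.60.

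**Detectable difference at 80% power (normal approximation).** (1.960 + 0.842) × √(2/20) × √(variance factor). Follow-up only: 2.802 × 0.3162 = 0.89 SD. ANCOVA at r = 0.7: 0.886 × √0.51 = 0.63 SD.

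**95% interval half-width.** Means over 5,000 simulated data sets per setting, with bivariate normal log steps. Follow-up only gives 0.64 SD at every r.

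| r | Variance, ANCOVA | Variance, change | Half-width, ANCOVA | Half-width, change | Detectable, ANCOVA |
|---|---|---|---|---|---|
| 0.3 | 0.91 | 1.40 | 0.61 | 0.75 | 0.85 |
| 0.5 | 0.75 | 1.00 | 0.56 | 0.64 | 0.77 |
| 0.6 | 0.64 | 0.80 | 0.52 | 0.57 | 0.71 |
| 0.7 | 0.51 | 0.60 | 0.46 | 0.49 | 0.63 |
| 0.8 | 0.36 | 0.40 | 0.39 | 0.40 | 0.53 |

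**Equivalent sample size.** 20/(1 − r²): adjustment makes 20 per arm worth about 27 unadjusted at r = 0.5, 39 at r = 0.7 and 56 at r = 0.8.

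**Power at an illustrative 0.6 SD.** The ranges span two simulation runs (5,000 and 3,000 data sets per setting).

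| r | Wilcoxon, follow-up | Wilcoxon, change | ANCOVA |
|---|---|---|---|
| 0.3 | 43–45% | 30–33% | 48–49% |
| 0.5 | 43–45% | 44% | 55–56% |
| 0.6 | 43–45% | 51% | 61–63% |
| 0.7 | 43–45% | 64–66% | 71–75% |
| 0.8 | 43–45% | 81% | 86% |

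Under the null, type I error was 4.2% to 4.9% for all three.

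**Does the gain depend on the log model?** In simulated skewed (lognormal) steps with a true effect of 0.8 log-scale SD, power for Wilcoxon on follow-up, Wilcoxon on raw change and rank ANCOVA was 0.68, 0.71 and 0.78 at r = 0.5; 0.66, 0.88 and 0.89 at r = 0.7; and 0.68, 0.97 and 0.97 at r = 0.8. Adjusting ranks for baseline keeps most of the gain.

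**Adding steps to the questionnaire model.** With baseline as an unconstrained outcome in a random-intercept model (baseline, weeks 12 and 24, compound symmetry), the week 12 contrast has relative variance 1.40, 1.00, 0.60 and 0.40 at r = 0.3, 0.5, 0.7 and 0.8, the same as a change score. Constraining baseline means to be equal across arms gives 0.91, 0.75, 0.51 and 0.36, the same as ANCOVA.

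**Chance imbalance.** The probability that two given arms differ at baseline by more than 0.3 SD is 2[1 − Φ(0.3/√(2/20))] = 0.34; for more than 0.5 SD it is 0.11.

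**The case against.** Steps serve a secondary aim, the plan disclaims power for them, and the rank sum test is a standard and valid choice for skewed data. Section VI.C is the operative methods text and, read literally, specifies follow-up levels; the Aim 3 sentence is a summary covering seven measures, and the word for an initial comparison suggests that more was intended. All of this is fair. It rules out any claim of bias or of a wrong sample size. It does not say which reading applies, and no further steps analysis is described.

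The size rests on assumptions. At r = 0.3 the gain is negligible, and a low r is plausible for inpatients. The half-widths and detectable differences assume 20 analysed per arm, whereas the enrolment margin covers losses only up to randomisation. If 16 per arm were analysed, the unadjusted half-width would be about 0.72 SD and the detectable difference 2.802 × √(2/16) = 0.99 SD. The relative variance factors would not change. The bivariate normal log model also favours log-scale ANCOVA, although the rank ANCOVA results point the same way.

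Naming a test does not forbid reporting an estimate. That stands: the gap is that the plan does not say which estimate and interval go with it.

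Finally, change scores do nearly as well as ANCOVA at r = 0.7 to 0.8. That is true, but they are no better than follow-up only at r = 0.5 and worse below it. With r unknown, covariate adjustment is the safer choice.

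**Conclusion.** The point holds. The Aim 3 text and Section VI.C do not agree on whether steps are compared as levels or as change, and the only named analysis makes no use of baseline as a covariate. This is a defect of clarity and precision, not of validity, and no stated power or sample-size figure changes. In each comparison above, baseline adjustment was at least as precise as both alternatives; its benefit over follow-up only runs from negligible at r = 0.3 to an interval about 40% narrower at r = 0.8 (0.39/0.64 = 0.61). That range depends on the assumed r, and the absolute figures also depend on complete follow-up of 20 per arm and roughly normal log steps. It should be corrected, because the data are already collected and the open choice between level and change is easily closed in advance.

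**What to change.** Reconcile the Aim 3 text in Section VI.A and B with Section VI.C, and name one main analysis of steps per day:

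- Analyse log (or square-root) steps with baseline steps, on the same scale, as a covariate, by ANCOVA at each visit or by a mixed model of weeks 12 and 24. A longitudinal model with baseline means constrained equal across arms is an alternative.
- Report PP versus MI and PP versus TAU with 95% confidence intervals, as ratios of geometric means if the log scale is used.
- State that week 12 is primary for Aim 3 too; the plan says so only in the Aim 2 text.
- Keep the Wilcoxon test or rank ANCOVA as a sensitivity analysis.
- Do not resolve the conflict by using raw change scores, or by adding steps to the questionnaires' random-intercept model with baseline as an unconstrained outcome.

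The cost is analysis wording only: no new data, visits or participants.

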## E. Data to be collected (See Table 1)

**Baseline Data:** Participants will complete the MOS, SSQ, SOM, LOT-R, PANAS, HADS, KCCQ, SRMA, and SF-12 in person and will receive an Actigraph accelerometer. They will be asked to begin wearing the accelerometer after their initial visit and prior to in-person visit #2 to measure their baseline physical activity.

Baseline information about enrolled participants will also be obtained from the participants, care providers, and electronic medical record as required for characterization of our population. This information will include data regarding medical history (history of coronary artery disease, acute coronary syndrome, coronary artery bypass graft, hypertension, diabetes mellitus, hyperlipidemia, body mass index, height, weight, and current smoking), current medical variables (renal function, N-terminal pro-B-type natriuretic peptide, left ventricular ejection fraction, NYHA class), medications, and sociodemographic data (age, gender,

race/ethnicity, living alone, education). This information will help us to ensure that the population we recruit is a representative population of patients suffering from HF so that the health behavior intervention we are testing is applicable to the broadest population of patients.

**Feasibility (primary study aim):** Feasibility will be measured by the number of PP sessions that were completed by participants. We will consider the intervention feasible if the majority of participants complete at least 7 of 12 exercises/sessions.

**Acceptability:** Following each PP exercise, participants will be asked to rate the ease of completion and subjective helpfulness of the exercise on a scale of 0 (very difficult/not helpful) to 10 (very easy/very helpful).

**Immediate impact:** To examine the immediate impact of the PP exercises on positive affect and optimism, participants will be asked to rate these psychological states before and after each exercise on a 10-point Likert scale (0 = not happy/optimistic, 10 = very happy/optimistic).

**Measurement of health behaviors.** We will assess three main health behaviors in this trial.

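### Free improvement: state in VI.C that the self-report models adjust for the pre-randomization score or share a common baseline mean, since the usual coding of change over time gives the less precise raw change contrast

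*Combined protocol and SAP*

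**What the plan says.** All references are to the combined protocol and SAP.

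- **Contrast.** Section VI.C: "we will compare between-group differences in change over time in all self-report measures" at 12 and 24 weeks. Sections VI.A and B frame the PP versus MI and PP versus TAU comparisons the same way: for Aim 2, "on changes in each of these psychological outcomes to assess the impact of the intervention compared to both an active control and TAU"; for Aim 3, "on changes in functional outcomes and health behaviors to assess the impact of the intervention".
- **Model.** Section VI.C: "using random effects regression models with a random intercept for each patient". The fixed effects are not written out.
- **Baseline data.** Section V.E: "Participants will complete the MOS, SSQ, SOM, LOT-R, PANAS, HADS, KCCQ, SRMA, and SF-12 in person". Table 1 puts these scales at the initial visit and randomization at the second visit, so all are pre-randomization measurements.
- **Time point and test level.** Under Aim 2, "The primary study endpoint will be 12 weeks", with 24 weeks secondary. Section VI.C: "All statistical tests will be two-tailed", at the 0.05 level.
- **Size.** Section VI.D: "We have performed power analyses assuming 20 participants in each group".

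Section V.E names PANAS positive affect as the main psychological outcome and KCCQ as the main functional outcome, so both fall under this model. Daily steps are compared by a rank sum test and are outside this point.

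**The concern.** An arm-by-visit term in a repeated-measures model is the ordinary way to express a between-group difference in change. If each arm keeps its own baseline mean, that term subtracts the whole observed baseline difference between arms. Randomization makes the expected baselines equal, so the observed difference is chance. Subtracting all of it adds noise and over-corrects: an arm that starts low by luck tends to show more improvement through regression to the mean. Adjusting for baseline, or imposing a common baseline mean, removes only the predictable part.

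Two things are at stake. With 20 per arm, precision for PANAS, KCCQ and the other scales is scarce, and the plan does not claim precision that is already available in the data. Also, section II looks for numerically larger improvement under PP than under the controls, and a chance baseline gap can create or mask a difference of that kind. Leaving the choice unstated also lets it be made after the data are seen.

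**Working it through.** **The plan's own figures.** They reproduce, and none concerns these contrasts.
- Feasibility (20 participants, 80% against 50%): rejecting at 15 or more of 20 gives exact two-sided alpha 0.041 and power 80.4%, as against at least 80% stated.
- Immediate impact (140 exercises, 20 people, correlation 0.5, d = 0.52): design effect 1 + (7 − 1) × 0.5 = 4 and effective n = 140/4 = 35. Power is 86.8% by the normal approximation or 83.1% by t on 19 df, as against over 80% stated.
- Enrollment: 60/(1 − 0.20) = 75.

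No SD, effect size, baseline to follow-up correlation or power is given for the self-report comparisons.

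**Inputs.** From the documents: n = 20 per arm, three arms, three visits, two-sided 0.05. Assumed: r is unknown, so a range is shown; complete data; equal variance at each visit and the single within-patient correlation that a random intercept implies. Results are in units of one outcome SD.

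**Formulas.** Let D0 and D12 be the differences between two arm means at baseline and week 12.
- Free arm baselines: the estimate is D12 − D0, with variance 2(1 − r) × 2/n.
- Common baseline mean or baseline covariate: the estimate is D12 − r·D0, with variance (1 − r²) × 2/n.
- Ratio: 2(1 − r)/[(1 − r)(1 + r)] = 2/(1 + r).
- Given a realized gap D0, the expected value of D12 is the true effect plus r·D0. The change contrast is therefore shifted by −(1 − r)·D0, and the adjusted contrast is not shifted.

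**Results at 2/n = 0.1.**

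| Assumed r | Variance, change | Variance, adjusted | Ratio | Excess SE of change |
|---|---|---|---|---|
| 0.4 | 0.120 | 0.084 | 1.43 | 20% |
| 0.5 | 0.100 | 0.075 | 1.33 | 15% |
| 0.6 | 0.080 | 0.064 | 1.25 | 12% |
| 0.7 | 0.060 | 0.051 | 1.18 | 8% |
| 0.8 | 0.040 | 0.036 | 1.11 | 5% |
| 0.9 | 0.020 | 0.019 | 1.05 | 3% |

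- Difference detectable with 80% power, (1.96 + 0.8416) × SE: 0.89 against 0.77 SD adjusted at r = 0.5; 0.69 against 0.63 SD at r = 0.7.
- Power for an assumed 0.5 SD difference: 35% against 45% at r = 0.5; 53% against 60% at r = 0.7.
- Chance gap: the SE of D0 is √(2/20) = 0.32 SD. A gap of that size shifts the change contrast by 0.5 × 0.316 = 0.16 SD at r = 0.5, or 0.3 × 0.316 = 0.09 SD at r = 0.7.

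**Check by simulation.** Mixed models were fitted to 150 simulated trials at each of two values of r. The free-baseline week-12 term equaled the raw change difference to rounding error. Its SD was 0.319, against 0.276 with the common baseline mean, at r = 0.5; and 0.260 against 0.243 at r = 0.7. Its slope on the baseline gap was −0.52 and −0.32 (theory −0.5 and −0.3), against about −0.02 with the constraint.

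**Cost of a covariate.** About 1 + 1/(60 − 3 − 2) = 1.018, or roughly 2% of variance.

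**The case against.** The best reply is that the plan does not specify a change-score test. It names a repeated-measures model in which baseline would normally be one of the responses, and it does not say that arm baselines are free. A model with a common baseline mean also estimates a difference in change, fits the quoted sentence and loses nothing. This stands. A reader might infer that the plan discards the baseline data, but the documents do not support that. What they show is that its use for precision is not stated.

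Second, the change contrast is valid. A reader might infer bias from the regression-to-the-mean argument, but the shift is conditional on the realized gap and averages to zero over randomizations. This also stands.

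Third, the gain depends on a correlation that the documents do not give, and at high r it is small. A reader might also infer that adjustment would rescue power: with an assumed 0.8 SD effect and r = 0.5, power rises from 72% to 83%. No such effect appears in the documents, and at 0.5 SD power is low either way for r = 0.5 or 0.7.

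Fourth, these are secondary comparisons in a pilot powered for feasibility and immediate impact, and section II expects only numerical advantages over the controls. That limits the consequence. It does not argue against a gain that costs almost nothing, and section VI.C still applies the 0.05 level to these tests.

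**Conclusion.** The point holds as a free improvement, not as an error. The plan frames all self-report contrasts as differences in change and states no use of baseline for precision. If the model is coded in the usual way, the standard error is about 20% to 3% larger than it needs to be for r from 0.4 to 0.9, and part of any chance baseline gap passes into the estimate. If a common baseline mean is imposed, there is no loss; the text leaves this open. The figures rest on an assumed r, complete data, equal variances across visits and 20 per arm. The contrast stays unbiased over randomization, and neither the feasibility conclusion nor any stated power figure changes.

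**What to change.** In section VI.C, write out the model for the self-report scales. Preferred: baseline, week 12 and week 24 as responses, with visit and arm-by-visit terms, a common baseline mean across the three arms, and the random intercept already planned (a constrained longitudinal model). Alternative: weeks 12 and 24 as responses, with the baseline score and a baseline-by-visit term as covariates. The two are close but not identical when follow-up is missing, because the covariate model drops anyone with no follow-up score while the constrained model keeps that person's baseline; name one in advance. Keep the PP versus MI and PP versus TAU contrasts at week 12, which the plan already names.

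The cost is a few sentences of analysis wording. No new data or visits are needed, and the covariate version gives up about 2% of variance at 60 randomized, less than it gains at every r shown.

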### Follow Ups:

**Follow-up phone calls (Week 12 and Week 24 [post randomization]).** At Weeks 12 and 24, a member of the study staff will call participants to repeat the self-report questionnaires that were administered at baseline. These questionnaires assess state optimism (State Optimism Measure; SOM), general optimism (LOT-R), positive affect (PANAS), overall health behavior adherence (MOS), anxiety/depression (HADS), HRQoL (SF-12), cardiac symptoms and HF-related QoL (KCCQ), medication adherence (SRMA), and sodium intake (SSQ). Participants will also be asked about cardiac-related hospital readmissions and cardiac rehabilitation, and to rate their overall satisfaction with the treatment they received for their cardiac condition over the course of the study on a scale of 0 (not at all satisfied) to 10 (completely satisfied). Finally, patients will be asked about their experience in the study, including any aspects of the intervention or study procedures that could be improved, during follow-up assessment. In sum, these scales should take approximately 30-40 minutes to complete. If participants would rather complete the follow-up questionnaires in written form rather than over the phone, we will send them a paper packet at the time of the follow-up.

**Training.** [name] (PI) has substantial experience in explaining and delivering PP exercises from their studies in cardiac and psychiatric patients. The PP exercises for this trial have been identified via published literature, or directly from researchers, and modified appropriately for this population. Additional text outlining the rationale and instructions for each exercise are located in the written packets for each exercise that are provided to participants. [name] will engage in several training exercises prior to study initiation. He will review the treatment manual and our team's prior training manuals related to these exercises. He will then complete all exercises to gain experience performing and reviewing each exercise.

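### If baseline, week 12 and week 24 are fitted in one model, the random intercept gives both change contrasts the same standard error, which is too small at week 24 whenever the baseline-to-week-24 correlation is below the three-pair average

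*Combined protocol and SAP*

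**What the plan says.** Under VI.C (Statistical methods), for the secondary aims, "we will compare between-group differences in change over time in all self-report measures" at 12 and 24 weeks, using "random effects regression models with a random intercept for each patient". No residual correlation structure, random slope, visit-specific variance or robust standard error is named, and the text does not say whether both follow-ups enter one model. "All statistical tests will be two-tailed", at the 0.05 level.

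The data come from three occasions. The scales are completed at the initial visit, and under Follow Ups (V.A), "At Weeks 12 and 24, a member of the study staff will call participants to repeat the self-report questionnaires that were administered at baseline".

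VI.A and B (Aim #2) ranks the time points: "The primary study endpoint will be 12 weeks, though we will secondarily assess the impact of the intervention on outcomes at 24 weeks as well". That ranking sits within a secondary aim; the trial's primary outcome is feasibility.

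On size, VI.D (Power analysis) says "We have performed power analyses assuming 20 participants in each group" and "we will enroll 75 participants with a goal of randomizing 60". The only within-person correlation in the documents, 0.5 in VI.D, concerns changes in ratings across exercises. It does not describe the scales across visits.

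**The concern.** A random intercept with independent residuals is a compound-symmetry model: one variance at every visit and one correlation for every pair of visits. When all three visits are fitted together, the model averages the three correlations and uses that average for both change contrasts. The gap from baseline to week 24 is about twice the gap between neighbouring visits, so a lower correlation over that gap is a reasonable expectation, though the documents do not establish it. In that case the true variance of the 24-week change exceeds what the model reports, its intervals are too short and its p-values too small.

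The model serves PANAS positive affect (primary psychological measure), KCCQ (primary functional measure) and the other self-report scales. Claims that an effect persists would rest on week 24, and the intervals from a pilot feed the planning of the next trial.

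**Working it through.** **The plan's own figures.** VI.D states "With 20 PP participants, we will have at least 80% power to detect a difference between our expected proportion" of 80% and a null of 50%. With an exact binomial test and n = 20, rejecting at 15 or more completers has an upper tail of 0.0207 (two-sided 0.041) and power 0.804. For immediate impact, 140 exercises from 20 people is 7 each; the design effect is 1 + (7 − 1) × 0.5 = 4, the effective n is 140/4 = 35, and power is Φ(0.52 × √35 − 1.96) = 0.868 (0.831 with t on 19 df). Both claims reproduce. Neither uses the 12/24-week model.

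**Inputs.** 20 per arm (VI.D); three visits (V.A); two-sided 0.05 (VI.C). Visit correlations are *assumed*, written as r(0–12) / r(12–24) / r(0–24), with equal variances and SD = 1.

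**Formulas** (complete data, categorical time by arm, all three visits in one model; r̄ is the mean of the three correlations, k is week 12 or 24):
- Model-based variance of a within-person change: 2(1 − r̄), the same at both visits.
- True variance: 2(1 − r(0–k)).
- Standard error of a two-arm difference in change: √(variance × 2/20).
- Ratio of model to true standard error: √[(1 − r̄)/(1 − r(0–k))].
- Actual type I error: 2[1 − Φ(1.96 × ratio)].

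**Example, 0.7/0.7/0.5.** r̄ = 1.9/3 = 0.633. Week 12: √(0.367/0.30) = 1.106, type I error 3.0%. Week 24: √(0.367/0.50) = 0.856, type I error 9.3%.

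| Assumed correlations | Ratio wk 12 | Type I wk 12 | Ratio wk 24 | Type I wk 24 |
|---|---|---|---|---|
| 0.7/0.7/0.7 (equal) | 1.00 | 5.0% | 1.00 | 5.0% |
| 0.7/0.7/0.65 | 1.03 | 4.4% | 0.95 | 6.2% |
| 0.7/0.7/0.6 | 1.05 | 3.9% | 0.91 | 7.4% |
| 0.7/0.7/0.5 | 1.11 | 3.0% | 0.86 | 9.3% |
| 0.6/0.6/0.36 | 1.10 | 3.2% | 0.87 | 9.0% |
| 0.8/0.8/0.64 | 1.13 | 2.7% | 0.84 | 10.0% |
| 0.6/0.7/0.5 | 1.00 | 5.0% | 0.89 | 8.0% |
| 0.5/0.7/0.45 | 0.95 | 6.3% | 0.90 | 7.6% |

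The week-24 ratio is below 1 exactly when r(0–24) is below r̄. The week-12 ratio exceeds 1 only when r(0–12) is above r̄.

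**Check by simulation, 0.7/0.7/0.49.** By formula the model standard error is √(0.74 × 0.1) = 0.272 at both visits, against true values √(0.60 × 0.1) = 0.245 and √(1.02 × 0.1) = 0.319. Over 40,000 simulated trials, rejection was 3.0% at week 12 and 9.9% at week 24. Sixty actual REML fits gave a mean standard error of 0.273 at both visits, against empirical SDs of 0.230 and 0.321. Giving each change its own variance, as an unstructured covariance does, brought rejection to 4.9% and 5.1%.

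**Separate models.** With baseline and one follow-up there is only one pair, so r̄ = r(0–k) and the ratio is 1. Two-visit fits at 0.7/0.7/0.49 gave mean standard errors of 0.246 and 0.322 against true 0.245 and 0.319.

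**Scale.** VI.A and B lists about 11 self-report scores (HADS subscales counted separately, SF-12 and SRMA once each), with two arm comparisons each: 22 tests at week 24. With no true effects, expected false positives are 22 × 0.05 = 1.1 at the nominal level, and between 22 × 0.062 = 1.4 and 22 × 0.100 = 2.2 over the 6.2% to 10.0% range.

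**The case against.** The strongest reply is that the error needs one joint model, and VI.C does not say there is one. It speaks of models in the plural at two time points, and Aim #2 treats week 24 as a secondary assessment. Fitting each follow-up separately with baseline fits the wording, and then there is no error. This stands, and the point is conditional on a joint fit.

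A second reply is that decay may be mild. Section V.E notes that dispositional optimism should in theory be stable, which suggests flatter correlations at least for LOT-R. This stands as to size: 0.7/0.7/0.65 gives only 6.2% at week 24.

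A reader might infer that the week-12 intervals are necessarily too wide, so that the main time point loses precision. The documents do not support this. Baseline may be taken on an inpatient unit, while follow-ups come by phone or on paper after the intervention period, so the two follow-ups could correlate more with each other than with baseline. The week-12 standard error is then correct at 0.6/0.7/0.5 and too small at 0.5/0.7/0.45.

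A reader might also infer that the 5% level fails at both visits. That does not follow: equal correlations or separate fits give 5%, and a 3% rate does not exceed the level.

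Finally, VI.D says the pilot is not designed to detect between-group differences in health behavior outcomes at 12 or 24 weeks, and a random intercept is a conventional choice. That limits the stakes, but VI.C still commits to significance tests on these scales.

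**Conclusion.** The concern holds conditionally. If the three visits are fitted together with default independent residuals, both changes get one standard error. The week-24 standard error is then too small whenever the baseline-to-week-24 correlation is below the average of the three, with type I error of about 6% to 10% for assumed correlations from 0.7/0.7/0.65 to 0.8/0.8/0.64. Week 24 was too narrow in every decay pattern checked. Under the patterns with equal neighbouring correlations and a lower baseline-to-week-24 correlation, week 12 has type I error of about 3% to 4%; under others it is correct or slightly anti-conservative (about 6%).

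These sizes rest on assumed correlations, equal variances and complete data. With complete data, only the reported standard errors and p-values move; the point estimates do not. The reach is the secondary-aim self-report comparisons. It would be wrong to infer that the trial's main conclusion is at risk: the feasibility criterion, the sample size, both power statements and the Wilcoxon test on steps do not depend on this model.

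**What to change.** In VI.C, replace the random intercept with an unstructured covariance over baseline, week 12 and week 24, with time categorical, fitted by REML with Kenward-Roger degrees of freedom. If that model does not converge, keep the random intercept with participant-clustered robust standard errors, and name the estimation method used with them.

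The cost is a change of wording in the analysis section and four extra covariance parameters: three variances and three covariances, six in place of two. That is feasible with about 60 participants at three visits. No visit, measure or sample size changes. If the correlations turn out equal, little is lost; in simulation with equal correlations of 0.7, allowing each change its own variance kept rejection at about 5% at both visits.
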